#### **Exclusion Criteria**

1. Dyads will be excluded if infants:
  - a. were born more than 6 weeks earlier than their estimated due date,
  - b. have any developmental delays or disabilities that make it difficult for them to eat, drink, or communicate,
  - c. attend regular daycare,
  - d. or will be younger than 4 months or older than 9 months at the time of the first ASL training.

## **4 STUDY PROCEDURES**

**4.1 Screening/Baseline Visit procedures:** Families will be recruited from a community sample through a variety of means, including email listservs, in-person interactions with study personnel, social media posting to local parenting groups, and publicly posted flyers. Those wishing to learn more about the study will contact our project manager, who will conduct screening and enrollment for those wishing to participate in the study.

**4.2 Intervention/Treatment procedures (by visits):** Intervention families will receive approximately 4 hours of ASL and development specific content related to language and feeding during home visits and phone calls. The initial in-home session with families will focus on teaching ASL signs indicative of hunger, thirst, and satiety. A video and placemat of mealtime signs will be left with families at the completion of the first visit. The remaining sessions, in-home over the next 3 months and by phone monthly thereafter for 6 months total, will focus on reinforcing ASL signing in addition to focused education on particular aspects of language development (receptive language preceding expressive language and increasing intentional communication), feeding development (such as hunger and fullness cues, fear of new foods, the importance of repeated food exposures, variations in intake from meal-to-meal, and the propensity to reject bitter tastes [many vegetables]), and appropriate portion sizes and variety for healthy growth.

In person visit lesson schedule (monthly from baseline at 4-9 months of age):

Visit 1 (baseline: T1): Signing with infants

Visit 2: Infant communication and responsive feeding

Visit 3: Nutrition, portion sizes, and neophobia

Visit 4 (T2): Infant intentionality

All families will be offered \$25, \$30, and \$35 at T1, T2, and T3 data collections, respectively. At the end of the study, control families will have the opportunity at the end of the 6-month study period to learn about what educational content was offered to the Experimental Group and study personnel will provide a booklet of this content to them and an ASL Signs of Feeding placemat if they wish. If subjects withdraw or are withdrawn from the study prior to arrival of the study personnel at their home for data collection, then no monetary incentive will be offered. If participating parent or infant withdraws or is withdrawn from the study once data collection has been initiated in their home, they will be offered one half of the possible monetary incentive amount for that visit for their attempt to participate. All subjects will be thanked for their interest and participation regardless of whether they complete all data collections.

See section 5 below for data collected at each visit.

- 4.3 Follow-up procedures (by visits):** Within a week of T1, T2, and T3 (6-months post-baseline), two 24-hour dietary recalls (to account for day-to-day variation) will be collected using NDS-R software by telephone five to 10 days apart. Intervention participants will also be contacted by the project manager with 48-hours of in-home study visits (1-4 above) to assess whether relevant intervention content was delivered.
- 4.4 Unscheduled visits:** N/A
- 4.5 Concomitant Medication documentation:** N/A
- 4.6 Rescue medication administration (if applicable):** N/A
- 4.7 Subject Completion/ Withdrawal procedures:** Subjects will complete the study at the completion of data collection associated with T3. At the end of the in-home data-collection visit at T3, all participants will be asked to provide feedback on their experiences with recruitment, interactions with study personnel, data collection, and anything else they would like to share about the study. If a participating dyad chooses to withdraw from the study or we are unable to reach them after three attempts for scheduling of visits or data collection, they will be withdrawn from the study, but their data will be kept for analysis. All subjects will be thanked for their interest and participation regardless of whether they complete all data collections.
- 4.8 Screen failure procedures:** If the subject and/or child do not meet inclusion criteria, then inform them that they do not meet inclusion criteria for this particular study, ask if they would be interested in being contacted about future studies, and thank them for their time.

## 5 STUDY EVALUATIONS AND MEASUREMENTS

Variables and Their Measurement	Measure	Data Source	T1	T2	T3	Alpha
Aims 1: Feasibility & Acceptability	Screening and Enrollment logs	Project Manager	X			
	Field Notes	RA's	X	X	X	
	Exit Interview	Mothers			X	
Aims 2 & 3						
Dyadic Feeding Responsiveness						
Mutual Responsiveness during	Responsiveness to Child Feeding Cues Scale (RCFCS) 	Infants & Mothers	X	X	X	0.85-0.94

Feeding						
Infant Eating Behavior						
Dietary Intake	Nutrition Data System for Research (NDS-R)	Mothers	X	X	X	
Eating Behavior	Child Eating Behavior Questionnaire-Toddler (CEBQ-T) 	Mothers	X	X	X	0.65-0.87
Infant Anthropometry						
Growth	Weight-for-length% & Z score	Infants	X	X	X	
Maternal Feeding Behavior/Beliefs	Infant Feeding Styles Questionnaire (IFSQ) 	Mothers	X	X	X	0.75-0.94 b
Autonomic Regulation	Respiratory Sinus Arrhythmia (RSA)	Infants & Mothers	X	X	X	
Additional Characteristics						
Infant						
Temperament	Revised Infant Behavior Questionnaire (IBQR) 	Mothers	X	X	X	0.91-0.92
Sex, Birthweight, & Gestational Age	Demographics	Mothers	X			
Maternal						
Parental Self-Efficacy	New Generalized Self-Efficacy Scale (NGSE) 	Mothers	X	X	X	0.85-0.88
Perception of Infant Intentionality	Infant Intentionality Questionnaire (IIQ) 	Mothers	X	X	X	0.77-0.87
Depression & Anxiety	Patient Health Questionnaire-4 (PHQ-4) 	Mothers	X	X	X	0.82
Demographic Characteristics	Demographics & Pregnancy History	Mothers	X			

**5.1 Efficacy Evaluation: N/A**

**5.2 Pharmacokinetic Evaluation (if applicable): N/A**

**5.3 Safety Evaluations:** Study visit confirmation will occur prior to study visits and assessment of self-reported health of parent and infant will be conducted prior to data collection. Study personnel will be on-site in subjects' homes for the duration of data collection and will monitor the response of subjects during data collection. Should any concerns arise during data collection, they will be addressed immediately by study personnel and the PI and Co-I will be notified as soon as possible if they are not on site. Though unlikely, should any concerns arise after data collection, subjects will be given the PI's contact information to share their concerns and the PI will address concerns directly or through appropriate referrals. Any concerns that arise over the course of the study will be recorded and aggregated as part of the feasibility data and shared with the research team and the IRB as necessary.

## **6 STATISTICAL CONSIDERATION**

### **6.1 Primary Endpoint**

T3 (6-months post-baseline) will serve as the primary endpoint for the study.

### **6.2 Secondary Endpoint**

There are no plans for a secondary endpoint, though safety will be monitored as discussed above in 5.3.

### **6.3 Statistical Methods**

Descriptive statistics will be calculated for each measure (see Aims 2 & 3 in Table of Measures, Section 5) at each time point by group. All analyses will be conducted using an intention-to-treat approach.

Preliminary analyses will be conducted to determine whether, despite randomization, the intervention and control groups exhibit a random imbalance at baseline on any measured variable. If important imbalances are found, the corresponding variable will be considered as a covariate in subsequent models to statistically correct for the imbalance. To evaluate the initial impact of the intervention longitudinally for each maternal and infant outcome listed above as primary, secondary, and the first two tertiary outcomes (i.e., more optimal growth, indicators of enhanced self-regulation of energy intake [NDS-R data compared to age- and sex-specific estimated energy requirements], reported infant feeding behavior and maternal feeding behaviors/beliefs, and observed dyadic feeding responsiveness), we will fit separate linear mixed-effects models. These could include a random coefficients model to examine the linear trajectories of the group-specific means across all available time points using the actually observed timing. The initial impact of the intervention will be formally assessed through a statistical hypothesis test of model parameter representing the difference in these slopes. More specifically, these models will include terms for the intervention group (as an indicator variable), actual time of data collection (as continuous weeks from baseline), and their interaction. An alternative modeling strategy would be to utilize mixed-effects model in a repeated measures context to examine the trajectories of the group-specific means across all available time points using the visit timepoint; these models will include terms for the intervention group (as an indicator variable), visit timepoint (as one or more indicators to reflect this categorical variable), and their interaction term(s). In this scenario, the initial impact of the intervention will be formally assessed through a statistical hypothesis test of linear contrasts of model parameters representing the between-group difference at each timepoint. Covariates identified above to correct for imbalance will be considered for inclusion in these models, as well as the factors stratified in the randomization, and the models will account for the repeated measures correlation structure. Statistical contrasts will also be constructed to estimate and test the changes over time separately for each intervention group. As useful information for planning subsequent studies, effect sizes for each measure will be calculated for each follow-up time point as the ratio of the mean difference between the intervention and the control groups to its standard deviation, as well as the producing the estimated correlation matrices across the repeated measures.

**6.4 Sample Size and Power:** Dyads will be randomized to either the intervention ( $n = 40$ ) or the control ( $n = 40$ ) group. Conservatively, a 20% attrition rate will be assumed, though less attrition will result in greater statistical power. Hence, we assume two-group, longitudinal comparisons of complete data on 32 dyads per group, as well as incomplete data (at some, but not all, time points), for analyses of each measure. Power calculations are performed with the POWERLIB20 SAS/IML module, which incorporates methods to calculate power for the general linear multivariate model, which is closely related to the general linear mixed model, assuming a first-order autoregressive correlation structure across the repeated measures with parameter  $\rho=0.9$ . We intend to estimate the power for the initial impact of the intervention through a test of mean linear change between the two groups across the three timepoints for each maternal and infant outcome in Aim 2 in separate multivariate models. The study will be well-powered to detect moderate changes in slope across the group trajectories over time. A linear difference of .4 SD by T3 with 32 dyads per group will provide statistical power exceeding .86 at the one-sided .05 significance level.

**6.5 Interim Analysis:** N/A

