**Study Phases**  
**Screening**

Screening: screening for eligibility and obtaining consent

---

Study Treatment Follow-Up	Study Treatment: study intervention/experimental treatment from baseline visit (T1) monthly until 3-months post-baseline (T2) Follow-up: 6-months post-baseline (T3)
Efficacy Evaluations	Primary efficacy evaluation measures: 
 
1. Infants in the intervention group will have more optimal growth (weight-for-length Z scores closer to 50th %) than the control group by T3.
 

Pharmacokinetic Evaluations	N/A
Safety Evaluations	
 
• Assessment of self-reported health of parent and infant prior to data collection
 
• Monitoring of parent's and infant's responses during intervention and data collection
 
• Reports of adverse events
 

Statistical And Analytic Plan	To evaluate the initial impact of the intervention longitudinally for each maternal and infant outcome listed in the primary, secondary, and first two tertiary outcomes above, we will fit separate linear mixed-effects random coefficients models. These will model the linear trajectories of the group-specific means across all available time points using the actually observed timing. The initial impact of the intervention will be formally assessed through a statistical hypothesis test of model parameter representing the difference in these slopes. More specifically, these models will include terms for the intervention group (as an indicator variable), actual time of data collection (as continuous weeks from baseline), and their interaction. Covariates identified above to correct for imbalance will be included, as well as the factors stratified in the randomization, and the models will account for the repeated measures correlation structure. Statistical contrasts will also be constructed to estimate and test the changes over time separate for each group.

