### **3.2 Allocation to Treatment Groups and Blinding**

Randomization will be stratified by age group (for developmental differences; 4-5-months-old, 6-7-months-old, and 8-9-months old). Computerized randomization lists will be generated by study

statistician and will be administered by the project manager. Study personnel who code videos of feeding interactions will be blind to group status.

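### Covariates are chosen by a baseline-imbalance screen with no list, threshold or stated form; synopsis and section 6.3 disagree on including the age stratum, and no stratum-by-time term is named

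*Combined protocol and SAP*

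**What the plan says.** Section 6.3 opens with preliminary analyses of whether "the intervention and control groups exhibit a random imbalance at baseline on any measured variable", and then: "If important imbalances are found, the corresponding variable will be considered as a covariate in subsequent models to statistically correct for the imbalance". It does not list the variables, name a test or define an important imbalance.

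On the models themselves, the two accounts differ:

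- Section 6.3: "Covariates identified above to correct for imbalance will be considered for inclusion in these models, as well as the factors stratified in the randomization".
- Protocol Synopsis, Statistical And Analytic Plan: "Covariates identified above to correct for imbalance will be included, as well as the factors stratified in the randomization". Nothing earlier in the synopsis identifies any covariates.

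Section 6.3 allows two models. The random-coefficients model has group, "actual time of data collection (as continuous weeks from baseline), and their interaction", and the effect is "formally assessed through a statistical hypothesis test of model parameter representing the difference in these slopes". The alternative treats visit as categorical and tests "linear contrasts of model parameters representing the between-group difference at each timepoint". The synopsis describes only the first. In neither place is a covariate or the stratum given an interaction with time or visit.

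Section 3.2 states: "Randomization will be stratified by age group". There are three bands (4-5, 6-7 and 8-9 months), and the reason given is developmental differences.

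**The concern.** Three things are at stake.

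- **Analyst choice.** Covariates picked from the trial's own data, over an open set of variables and with no threshold, mean the primary model is not fixed before the groups are compared.
- **Whether the adjustment does anything.** The slope model tests a difference in change over time. A covariate that is constant within an infant and enters only as a main effect shifts an infant's level, not its change. The correction that section 6.3 promises would then not reach the tested parameter.
- **Use of the stratification.** Age was stratified because development differs by age, so change over six months may differ by stratum. If it does, and the model has no stratum-by-time term, the between-stratum spread in change stays in the error. The standard error is then too large for a design that has already balanced it.

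**Working it through.** **Inputs from section 6.4:** 40 dyads per arm, 20% attrition leaving 32, AR(1) with rho = 0.9, a 0.4 SD difference by T3, one-sided .05, stated power above .86. With equal spacing the T1-T3 correlation is 0.9² = 0.81.

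**1. The plan's power figure.** SD of T1-T3 change = √(2(1 − 0.81)) = 0.616. With 32 per arm this gives power .829 (normal) or .822 (t). Adjusting for baseline, SD = √(1 − 0.81²) = 0.586, which gives .861 or .854. The stated figure is recovered with baseline adjustment but not with the plain linear-change test. That is a separate matter and is not disputed here; .82 is the reference value below.

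**2. Main effect in the slope model.** Centre time at its weighted mean under the model covariance. With common visits and complete data, group × centred time is then orthogonal to anything constant within a dyad, so a main effect cannot move the slope difference. A numerical check used 600 simulated trials, 40 per arm, known AR(1) covariance and no treatment effect. Assumed, and not in the documents: a covariate imbalanced by 0.5 SD, with effect 0.3 SD on level and 0.3 SD on change to T3. The expected spurious slope difference is 0.5 × 0.3 = 0.15 SD by T3, and the expected spurious T3 difference is 0.5 × (0.3 + 0.3) = 0.30 SD.

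| Tested quantity | Unadjusted | Main effect | Covariate × time (or visit) |
|---|---|---|---|
| Slope difference, complete data | 0.1605 | 0.1605 | 0.012 |
| Slope difference, 20% dropout | 0.147 | 0.148 | 0.001 |
| T3 difference, categorical visit, complete data | 0.314 | 0.088 | 0.013 |

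With complete data the largest change in any one slope estimate was about 1e-16; with dropout it was 0.027. A further run with dropout and irregular visit times gave 0.130, 0.131 and −0.012.

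**3. Omitting stratum-by-time.** Take 11/10/11 dyads per arm by stratum and mean change differing by δ between adjacent strata (assumed). The between-stratum variance in change is δ² × 22/32. Balance by arm keeps this out of the true error of the group contrast, but without the term it inflates the estimated error.

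- True SE = √(0.38 × 2/32) = 0.154, where 0.38 = 2(1 − 0.81).
- Estimated SE without the term = √((0.38 + 0.6875δ²) × 2/32).
- At δ = 0.5: added variance 0.172, estimated SE 0.186. With critical t of 1.670 (62 df), the rejection boundary is 0.310. Alpha ≈ P(Z > 0.310/0.154) = .022; power ≈ P(Z < (0.4 − 0.310)/0.154) = .72.

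Simulation (20,000 or more trials) agrees:

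| δ (SD) | Without stratum × time: alpha / power | With it: alpha / power |
|---|---|---|
| 0.5 | about .023 / .72 | about .05 / .82-.83 |
| 0.3 | about .037 / .78 | about .05 / .82 |
| 0.1 | .049 / .817 | power .821 |

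**4. Chance of flagging something.** If imbalance were judged by independent tests at .05, P(at least one flag) = 1 − .95^k: 40% for k = 10 and 54% for k = 15. This is illustration only, since section 6.3 names no test or level.

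**The case against.** A reader might infer more than the documents support, and the counter-case is right on several points.

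- **That covariates enter as main effects.** The documents do not say so. Considering a variable for inclusion does not rule out a time interaction. The defect is that the form is unspecified.
- **That adjustment cannot work in this trial.** This holds only for the slope model. In section 6.3's alternative model a main effect cuts the spurious T3 difference from 0.314 to 0.088, and section 6.1 makes T3 the primary endpoint, so that model is not peripheral.
- **That the plan leaves the stratum optional throughout.** The synopsis says it is included. The supported finding is a contradiction.
- **That the trial loses ten points of power.** A 0.5 SD step between adjacent strata is 1.0 SD between youngest and oldest in 6-month change. Nothing in the documents supports that for a growth-reference Z score, or for intake compared with age- and sex-specific requirements. If rho = 0.9 already reflects mixed ages, omitting the term at 0.5 SD still gives power .89 (against .97 with it), which is a forgone gain and not a shortfall. The alpha error is conservative in every case.

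What remains is not answered: the screen is open-ended, the two sections conflict, the form is missing, and in the slope model the form decides whether the adjustment has any effect.

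**Conclusion.** The concern holds in a limited form. Covariate selection is data-dependent with no list or threshold, and the synopsis and section 6.3 conflict on inclusion. Because neither states the form, the plan does not secure the correction it promises. For the slope model the main-effect result is exact with common visits and complete data, and close to exact with dropout. For the categorical-visit model a main effect corrects part of an imbalance.

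The cost of omitting stratum-by-time depends on a quantity the documents do not give. It runs from negligible (0.1 SD or less between adjacent strata) to about ten points of power (0.5 SD), and the error is always towards a conservative test. The change should be made because it is cheap and removes discretion, not because a power shortfall has been shown.

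**What to change.** In both the synopsis and section 6.3:

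- State that every primary model includes the age stratum and stratum × time (or stratum × visit in the categorical model).
- Remove the imbalance screen as a model-building step and report baseline tables descriptively. Any imbalance-driven adjustment becomes a labelled sensitivity analysis, entering with its time interaction.
- Adjust for the baseline outcome only in a form that affects the tested parameter. Either take T2 and T3 as responses with baseline and baseline × visit as covariates, or keep T1 as a response and constrain baseline means equal across arms. Adding baseline as a main effect to a slope model that already has T1 as a response would fail for the reason shown in step 2 of the working.

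The cost is wording plus two degrees of freedom for stratum × time and two for the stratum main effects. In the categorical model, stratum × visit takes (3 − 1) × (3 − 1) = 4. If change does not differ by stratum, the power cost is negligible (.82 with or without the term).

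### No single primary test is designated: the synopsis commits to a slope difference, section 6.3 also allows group differences at each visit, and neither plans adjustment for the T1 outcome

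*Combined protocol and SAP*

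**What the plan says.** Four places bear on which result answers the primary question.

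- **Protocol Synopsis, Statistical And Analytic Plan.** It is firm: "we will fit separate linear mixed-effects random coefficients models", and "The initial impact of the intervention will be formally assessed through a statistical hypothesis test of model parameter representing the difference in these slopes".
- **Section 6.3.** The same model becomes optional: "These could include a random coefficients model to examine the linear trajectories of the group-specific means across all available time points". Its formal test is a "statistical hypothesis test of model parameter representing the difference in these slopes". The text then continues: "An alternative modeling strategy would be to utilize mixed-effects model in a repeated measures context". That second model has group, categorical visit and their interaction, and its formal test is a "statistical hypothesis test of linear contrasts of model parameters representing the between-group difference at each timepoint". No criterion is given for using one model or the other, and no multiplicity rule covers the visits.
- **Section 6.1.** "T3 (6-months post-baseline) will serve as the primary endpoint for the study". It names a time but no test.
- **Section 6.4.** Power is given for linear change across the three visits only.

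On baseline, both models take all visits as outcomes, so T1 has its own free group difference. The only provision for adjustment is in section 6.3: "If important imbalances are found, the corresponding variable will be considered as a covariate in subsequent models". No threshold for importance is stated.

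**The concern.** The two permitted tests ask different questions of the same data and can disagree. If the plan does not say which one decides, the choice can be made once results are known, and the nominal 5% no longer applies. The tests also use T1 differently. The slope test uses it by differencing, while the T3 contrast in the categorical model, with an unconstrained T1 group difference, leaves it unused. Section 6.4 assumes that T1 predicts T3 strongly, so the second option could forgo much of the precision on which the sample size rests.

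**Working it through.** **Inputs, all from section 6.4:** 32 dyads per group with complete data; a linear difference reaching 0.4 SD at T3, hence 0, 0.2 and 0.4 at T1, T2 and T3; AR(1) with ρ = 0.9; one-sided α = .05; stated power above .86. I assume equally spaced visits, so r = corr(T1,T3) = 0.9² = 0.81, and unit SD at each visit.

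**Formula.** Noncentrality = 0.4 / (s·√(2/32)) = 0.4 / (0.25·s), where s is the SD of the quantity compared:

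- Slope. With three equally spaced visits the weights are −1, 0, 1, so s = √(2(1−r)) = √0.38 = 0.616 and the noncentrality is 2.596.
- Unadjusted T3 difference. s = 1 and the noncentrality is 1.600.
- T3 difference adjusted for T1. s = √(1−r²) = √(1−0.6561) = 0.586 and the noncentrality is 2.728.

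| Test | Power, normal approximation | Power, noncentral t |
|---|---|---|
| Slope difference | .829 | .822 |
| Unadjusted T3 difference | .482 | .475 |
| T1-adjusted T3 difference | .861 | .854 |

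**The plan's own figure.** With 32 per group the free-baseline slope test falls 3 to 4 points short of .86. A test that conditions on T1 gives .861 by the normal approximation. The slope test gives .866 with 36 per group, and section 6.4 also counts on some incomplete data, so I cannot tell which calculation lies behind the stated figure. Neither route gets the unadjusted T3 contrast near it; that contrast would need about 93 completers per group for .86.

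**Dependence on the correlation** (noncentral t, 32 per group):

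| AR(1) ρ | corr(T1,T3) | Slope | Unadjusted T3 | T1-adjusted T3 |
|---|---|---|---|---|
| 0.9 | 0.81 | .82 | .475 | .85 |
| 0.7 | 0.49 | .47 | .475 | .57 |
| 0.5 | 0.25 | .36 | .475 | .50 |

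Slope and unadjusted T3 are equal when 2(1−r) = 1, that is r = 0.5. The adjusted variance 1−r² is below 1 for any nonzero r. It is below 2(1−r) for any r < 1, because 2(1−r) − (1−r²) = (1−r)². So, for equal variances, the adjusted contrast has the smallest variance whatever the correlation; the one degree of freedom it costs is negligible here.

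**Type I error if the favourable test is reported.** Under the null, the slope and T3 statistics correlate (1−r)/√(2(1−r)) = 0.19/0.616 = 0.308. The chance that at least one passes one-sided .05 is about .093. If T2 may count as well, it is .111 (simulation under the same covariance). Over assumed r from 0.3 to 0.9, the slope-or-T3 figure runs from .085 to .094.

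**Disagreement under the assumed effect.** At ρ = 0.9, the slope and unadjusted T3 tests reach opposite conclusions in about 45% of simulated trials.

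**The case against.** Several points on the other side are fair.

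- **One model or the other.** Section 6.3 presents the second model as an alternative, not as an additional test. The 9% arises only if the choice follows sight of the data, and the 11% also needs a T2 result to count although section 6.1 names T3. This stands: the figures are worst cases. The text does not exclude them, but a reader who inferred that the plan will run at double its nominal error would go beyond it.
- **Baseline is not ignored altogether.** The slope test uses T1 by differencing, and failing to condition on it costs only about 3 points (.822 against .854). The imbalance clause could also bring the T1 outcome in as a covariate. Both points stand. But that clause is triggered by the data and has no threshold, so it is a further open choice and no substitute for planned adjustment.
- **Half the power.** A reader might infer that the categorical option generally has half the power of the slope test. It does not. At ρ = 0.9 the ratio is .475/.822, or 58%; near r = 0.5 the two are equal, and below that the slope test is weaker. The figure also rests on a stand-alone T3 contrast. A joint 3-df test of all visits would have power of about .62 at α = .05.
- **Early-stage study.** The trial is labelled Stage 1 and assesses initial impact. That limits how much hangs on one p-value. It still names a primary outcome, makes a power claim and describes its tests as formal, so the deciding test should be named.

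**Conclusion.** The plan leaves the primary test open. The synopsis and section 6.3 disagree, section 6.3 gives no selection rule, and neither permitted option plans adjustment for the T1 outcome. On the plan's own assumptions the choice matters: power is about .82 for the slope and .48 for the unadjusted T3 contrast, against .85 for a T3 contrast that conditions on T1. The large loss belongs to the categorical option read as a separate T3 contrast, and its size depends on ρ = 0.9. What does not depend on ρ is that the T1-adjusted contrast is best. The possible inflation to about 9% (slope or T3) or 11% (T2 as well) is conditional on choosing after seeing the results. The documents do not show that this is intended.

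**What to change.** In section 6.3 and in the synopsis, name one primary test for weight-for-length Z: the group contrast at T3 from the categorical-time mixed model, with age stratum included and T1 conditioned on, either as a covariate or by constraining the group means to be equal at T1. This agrees with section 6.1. A slope test that conditions on T1 would be practically equivalent under the plan's assumptions (noncentrality 2.728 for both), so the essentials are one named test and planned use of T1. Make T2 and the other model supportive, and drop the group test at T1. Section 6.4 should then state power for the named test.

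Two limits apply. Do not extend this to RSA, which is exploratory and whose hypothesis is an association with feeding responsiveness, not a group difference. And do not adjust for T1 feeding observations or dietary recalls as now scheduled. Section 10 places the T1 video after the first lesson, and the recalls are made by telephone around that visit, so those T1 values may already reflect the intervention. Rewording the analysis cannot cure that. T1 weight and length are also measured after the lesson, but a lesson at the same visit should not alter them.

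For the primary outcome the cost is wording only: no new data and no additional dyads.
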